**Randomized Double Blinded Study Comparing Timing of PEC Block  
for Post-Operative Pain in Bilateral Mastectomy Patients**

NCT Number: 03653988

[name]

Document Date: October 3, 2018

The current standard of care at the [REDACTED] is to receive a pectoralis nerve block PEC I/II block prior to surgery for mastectomy and reconstruction cases. We will compare whether patients will have better pain control if they were to receive (PEC I/II block) before surgery or after the mastectomy. Patients undergoing mastectomies at the [REDACTED] receive general anesthesia and a regional block for pain control. The most commonly employed regional anesthetic technique is a PECS I/II block to anesthetize the pectoral, intercostobrachial, third to sixth intercostal and long thoracic nerves. The PECS I/II blocks are pectoralis field blocks where local anesthetic medication is injected under ultrasound guidance between the tissue planes of pectoralis major and minor muscles (PECS I) and in the plane of the serratus anterior muscle at the level of the third rib (PECS II). We will randomize patients into two groups and blind the patient and the research assistant collecting the data. Group I will have the block performed after induction of general anesthesia and prior to surgical incision by the anesthesiologist. Group II will have the block administered by the surgeon after mastectomy is performed and before reconstruction. On the day of surgery, we will have patients fill out forms to measure pain catastrophizing and depression and anxiety. We would like to measure if there is any difference in postoperative pain scores (visual analogue scale)-immediately post-surgery in post-anesthesia care unit(PACU), and then on the admission unit every 4 hours for the first twenty four hours or on discharge (whichever time-point occurs sooner) and we will collect the average pain scale of the day on post-op day (POD) 2,3,5 and 7 via patient communication electronic message in RedCap. We will also measure intraoperative and post-operative narcotic use (converted to morphine equivalents), post-operative nausea and vomiting, length of (PACU) stay. In addition, we will collect pain scores and pain catastrophic scale on POD 14 after surgery at their clinic visits to the surgeon. Other data collected will include time taken to perform block, post-operative infection rate and post-operative flap necrosis rate.

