**Randomized Double Blinded Study Comparing Timing of PEC Block
for Post-Operative Pain in Bilateral Mastectomy Patients**

NCT Number: 03653988

[name]

Document Date: October 3, 2018

Statistical Plan

The primary objective is to evaluate whether administration of a PEC I/II block post-mastectomy reduces average pain scores during post anesthesia care unit (PACU) and inpatient stay when compared to administration pre-mastectomy. Accordingly, a sample size of 34 patients ensured 80% power to detect a mean difference in pain scores of at least 2 as being clinically significant. Calculations were based on 1:1 randomization, a common standard deviation of 2, and using a two-sided, two-sample t-test evaluated at a 5% significance level. The secondary outcomes were average pain scores on POD 2, 3, 7, 14, 60 and 180 days, postoperative narcotic requirements, PACU and inpatient length of stay, complications, and readmission rates.

Chi-squared or Fisher's exact tests (where appropriate) were used to compare categorical variables, and Wilcoxon rank sum tests were used to compare continuous variables between treatment groups. Linear mixed effects regression models were used to assess treatment group differences in terms of pain scores, number of pills taken post-operatively, and PCS scores. Random effects were included to account for the longitudinally correlated nature of repeat assessments within a patient over time. All tests were two-sided and assessed for significance at the 5% level using SAS v9.4 (SAS Institute, Cary, NC).

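### The trial is framed as a comparison of block timing, but operator type changes with timing in every patient, so a difference cannot be credited to timing alone

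*Protocol*

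**What the plan says.** The contrast is named by time point alone in three places:

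- Protocol title: "Randomized Double Blinded Study Comparing Timing of PEC Block".
- Protocol aim, in the opening lines: whether patients have "better pain control if they were to receive (PEC I/II block) before surgery or after the mastectomy".
- SAP, Statistical Plan, first paragraph: the primary objective is whether "administration of a PEC I/II block post-mastectomy reduces average pain scores" over the PACU and inpatient stay, "when compared to administration pre-mastectomy".

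The group definitions in the Protocol fix the operator as well as the time. For the first arm: "Group I will have the block performed after induction of general anesthesia and prior to surgical incision by the anesthesiologist". For the second: "Group II will have the block administered by the surgeon after mastectomy is performed and before reconstruction". There are only these two arms.

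On analysis, the second paragraph of the Statistical Plan says "Linear mixed effects regression models were used to assess treatment group differences in terms of pain scores". It mentions no operator term. Neither document describes standardization of the block between operator types, and neither says that the comparison is of timing and operator combined.

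**The concern.** Two features of the intervention change together from one arm to the other: the time of the block and the specialty of the person performing it. Randomization balances patient characteristics between arms, but it cannot separate two components that are always assigned together. Blinding the patient and the research assistant limits reporting and assessment bias, and does not separate them either.

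What is at stake is the meaning of the primary result. If the arms differ, the objective as worded would attribute the difference to timing, although part or all of it could come from operator type. If they do not differ, the same wording would suggest that timing does not matter, although opposing timing and operator effects could have cancelled.

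**Working it through.** **Inputs.** From the SAP, Statistical Plan, first paragraph: 34 patients, 1:1 allocation (17 per arm), difference 2, common SD 2, two-sided two-sample t-test at 5%, 80% power. From the Protocol's group definitions: time and operator in each arm. The documents give no operator effect, so any value used for one below is an assumption.

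**Step 1. Reproduce the plan's figure.** Standard error of the difference = 2 × √(2/17) = 0.686. Noncentrality = 2 / 0.686 = 2.92 on 32 degrees of freedom. Exact noncentral-t power is 80.7% at 17 per arm and 78.1% at 16 per arm. The smallest adequate size is therefore 17 per arm, or 34 in total, as the SAP states. The sample size is not in question.

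**Step 2. Lay out the design.**

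| | Anesthesiologist | Surgeon |
|---|---|---|
| Before incision | Group I | no patients |
| After mastectomy | no patients | Group II |

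**Step 3. What the group difference estimates.** Write mean pain = a + τT + ωO, with T = 1 for a post-mastectomy block and O = 1 for a surgeon's block.

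- Group I (T = 0, O = 0): mean a.
- Group II (T = 1, O = 1): mean a + τ + ω.
- Difference, Group II minus Group I: τ + ω.

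The design matrix has rows (1, 0, 0) and (1, 1, 1) only. Its rank is 2 with 3 columns, and T and O have correlation 1.0. The rank stays 2 at 17, 170 or 1,700 per arm. An operator-type term in the mixed model would duplicate the group term, so adjustment cannot help.

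**Step 4. Precision.** With t(0.975, 32 df) = 2.037, the 95% half-width for τ + ω is 2.037 × 0.686 = 1.40 points. This uses the planning t-test and SD; the SAP's mixed model may give a somewhat different width. To turn it into a statement about τ, a limit on ω must be brought in from outside the trial. If |ω| ≤ d is assumed, the interval for τ is the estimate ± (1.40 + d): ±1.90 for d = 0.5, ±2.40 for d = 1.0, ±2.90 for d = 1.5.

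**Step 5. Illustration with assumed operator effects** (planning t-test, 17 per arm, SD 2):

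| Assumed operator effect (points) | Chance of a significant difference if timing has no effect | Power if timing has a 2-point effect and the operator effect opposes it |
|---|---|---|
| 0 | 5.0% | 80.7% |
| 0.5 | 10.9% | 56.4% |
| 1.0 | 29.3% | 29.3% |
| 1.5 | 56.4% | 10.9% |

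The middle column is not an inflated error rate for the strategy comparison, since in those rows the strategies do differ. It is the chance that a difference due only to operator type would be reported under a timing objective.

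**The case against.** The strongest reply is that this is a pragmatic comparison of two care pathways and that the operator is disclosed. Both group definitions name the operator in the same paragraph as the aim, and the SAP's models assess treatment group differences, which is the strategy contrast. On this reading, pre- and post-mastectomy are shorthand for the two defined groups, and operator belongs to the strategy rather than being a nuisance factor. Neither document explicitly promises to isolate timing, and neither gives reason to think that an operator effect exists.

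Much of this stands. The strategy comparison is valid, no bias has been shown, and the figures in step 5 are illustrations. The rank result follows directly from any two-arm design in which two attributes are tied to arm, and the power and interval describe the contrast that is sound rather than the size of the defect.

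It does not remove the point. If the intended question is about pathways, the title, aim and primary objective do not say so. Naming the operator in the arm definitions does not limit a conclusion stated in terms of timing. The documents also give no basis for taking the operator effect as zero.

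**Conclusion.** The concern holds, with high confidence. Carried out exactly as written, the trial can show whether an anesthesiologist's block before incision and a surgeon's block after mastectomy lead to different pain scores. It cannot show how much of a difference, or of a null result, is due to timing. The data alone place no bound on the timing part; the planned ±1.40 points applies to timing and operator combined.

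This rests only on the group definitions and needs no assumption about the size or direction of an operator effect. It is a problem of identifiability and interpretation, and it leaves the sample size and the randomized comparison intact. It should be corrected because it concerns the primary objective and no planned analysis can repair it.

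**What to change.** - Restate the primary objective and the permitted conclusion as anesthesiologist-performed PEC I/II block before incision versus surgeon-performed PEC I/II block after mastectomy.
- Add one sentence to the SAP, and carry it into the report of results, saying that the comparison does not isolate timing from operator type.
- Interpret any between-group comparison of block performance time, which the Protocol lists among its other data, with the same limit.
- Changing the title to match is desirable but optional.

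These are changes of wording. Conduct, sample size, analysis and patient care stay as they are. The price is a narrower claim, which is the one the design supports.

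### No preoperative pain score is listed, which costs some precision and leaves late pain without a reference value, but does not bias the randomized comparison

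*Protocol*

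**What the plan says.** The protocol's single descriptive paragraph gives the baseline assessments in one sentence: "On the day of surgery, we will have patients fill out forms to measure pain catastrophizing and depression and anxiety". Pain intensity is not among them.

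Pain scores, in the order the protocol lists them, are:

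- in PACU: "postoperative pain scores (visual analogue scale)-immediately post-surgery in post-anesthesia care unit(PACU", then every 4 hours on the ward up to 24 hours or discharge;
- at home: "we will collect the average pain scale of the day on post-op day (POD) 2,3,5 and 7";
- at the clinic visit: "we will collect pain scores and pain catastrophic scale on POD 14 after surgery".

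Both arms have had their block before the PACU score: one before incision, the other between mastectomy and reconstruction.

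In the SAP (Statistical Plan, first paragraph), the primary question is whether the later block "reduces average pain scores during post anesthesia care unit (PACU) and inpatient stay". The secondary pain outcome is "average pain scores on POD 2, 3, 7, 14, 60 and 180 days". For the sample size, the SAP says that "a sample size of 34 patients ensured 80% power" to "detect a mean difference in pain scores of at least 2 as being clinically significant". The second paragraph compares pain scores between arms with linear mixed models that include random effects for repeated measures. It names no baseline covariate.

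**The concern.** Catastrophizing is listed on the day of surgery and again on POD 14, so a secondary psychological scale has a pre-treatment value while the primary outcome has none. Catastrophizing does not measure pain intensity and cannot stand in for it. The random effects describe correlation among a patient's postoperative scores; they do not adjust for pain before surgery.

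Two things are at stake. First, with 17 patients per arm the groups can differ by chance in preoperative pain, and without a score that difference can be neither seen nor adjusted for. Second, a patient's pain at day 60 or 180 may be new or may have been there before the operation, and no later analysis can tell which. A preoperative score not taken before surgery cannot be obtained prospectively afterwards.

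**Working it through.** **Inputs from the SAP:** difference 2, common SD 2, 1:1 allocation, two-sided two-sample t-test at 5%, 34 patients (17 per arm), 80% power.

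**Assumed input:** r, the correlation between preoperative pain and the postoperative average. The documents give none; I use 0.1, 0.2, 0.3 and 0.5.

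**1. Reproduce the plan's figure.** Noncentrality = 2 / (2 × √(2/17)) = 2.915, with 32 degrees of freedom and critical t 2.037. Power is 80.7% at 17 per arm and 78.1% at 16 per arm. The smallest size reaching 80% is therefore 17 per arm, or 34 in total, as stated. (The normal approximation gives 16 per arm, or 32.) None of this needs a baseline score.

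**2. Validity without a baseline score.** The unadjusted t-test was simulated with no treatment effect, 17 per arm, 40,000 runs each at r = 0.3, 0.5 and 0.7. The mean estimated difference was within 0.01 of zero, and type I error was 4.9% to 5.0%.

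**3. Power with adjustment.** Residual SD = 2 × √(1 − r²). One degree of freedom goes to the covariate, leaving 31.

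**4. Chance imbalance.** The standard error of the between-arm difference in baseline pain is √(2/17) = 0.343 baseline SD, so the 95% limit is 1.96 × 0.343 = 0.67 SD. An imbalance passes into the outcome only through r: shift = r × 2 × 0.672 points.

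| r (assumed) | Residual SD | Power at 34, adjusted | Total N for 80% | Shift at 95% imbalance (points) |
|---|---|---|---|---|
| 0.1 | 1.99 | 81.0% | 34 | 0.13 |
| 0.2 | 1.96 | 82.2% | 34 | 0.27 |
| 0.3 | 1.91 | 84.1% | 32 | 0.40 |
| 0.5 | 1.73 | 90.3% | 26 | 0.67 |

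**5. A caveat on step 3.** The power column treats the arms as balanced on the covariate. Correcting for imbalance multiplies the variance of the adjusted difference by about 1 + 1/30 on average (32 within-arm degrees of freedom, less 2). Power then becomes about 79.7%, 80.9%, 83.0% and 89.4%. The tabled values are thus about one percentage point generous, and at r of 0.2 or below there is in effect no gain.

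**The case against.** The strongest reply is that nothing here is an error. The trial is randomized, the objective compares arms rather than attributing pain within a patient, and the outcome SD of 2 used for the sample size already contains whatever variation preoperative pain contributes. Covariate adjustment is optional. The benefit depends on an r that the documents do not supply. They also do not say how common preoperative pain is in these patients; if most score near zero, the item would add almost nothing. Nor do the documents make persistent postsurgical pain an objective. All of this stands, and it limits the point to an improvement.

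A second reply is that the protocol is a one-paragraph summary and visibly incomplete. The SAP analyses pain at days 60 and 180 and readmissions, none of which the protocol lists. This also stands: the documents support saying that no preoperative score is listed, not that none was taken.

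A reader might go further and infer that the pain comparison is confounded by pre-existing pain, that any imbalance passes in full into the result, or that the sample size is too small. The documents do not support these readings. Steps 1 and 2 show a reproducible sample size and a valid test, and step 4 shows that an imbalance is scaled down by r.

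What the reply does not remove is the descriptive gap at days 60 and 180, and the thin margin in power. Losing one patient per arm takes the design to 78.1%, and a covariate with r of 0.3 or more would give some room.

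**Conclusion.** The point holds as a low-priority improvement. No preoperative pain score is listed and no baseline covariate is named. The cost is in precision, protection against chance imbalance, and interpretation of late pain scores; the primary comparison and its type I error are sound.

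The size depends wholly on the assumed r. The gain is negligible at 0.2 or below, about 3 percentage points of power at 0.3 and about 10 at 0.5, with each tabled power roughly one point generous. An unlucky imbalance at the 95% limit would move the unadjusted difference by 0.13 to 0.67 points against the target of 2. These figures further assume a linear relation, approximately normal scores, and the SAP's SD of 2. They apply to the single average used for the sample size, not to each time point in the mixed models.

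**What to change.** Add one pain item to the day-of-surgery forms, on the same VAS as in PACU, and state in the SAP that it enters the mixed models for pain as a fixed covariate. The number of patients need not change.

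The cost is one form item, one SAP phrase and one degree of freedom. It needs no extra visit, staff or procedure. The return will be small if r is 0.2 or below or most patients score near zero.

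The SAP is written in the past tense, so collection may already be over. In that case, check whether a preoperative score was recorded although the documents do not list it. If none exists, report its absence as a limitation, especially for days 60 and 180, and do not describe pain at those times as new since surgery.

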**Randomized Double Blinded Study Comparing Timing of PEC Block
for Post-Operative Pain in Bilateral Mastectomy Patients**

NCT Number: 03653988

[name]

Document Date: October 3, 2018

Statistical Plan

The primary objective is to evaluate whether administration of a PEC I/II block post-mastectomy reduces average pain scores during post anesthesia care unit (PACU) and inpatient stay when compared to administration pre-mastectomy. Accordingly, a sample size of 34 patients ensured 80% power to detect a mean difference in pain scores of at least 2 as being clinically significant. Calculations were based on 1:1 randomization, a common standard deviation of 2, and using a two-sided, two-sample t-test evaluated at a 5% significance level. The secondary outcomes were average pain scores on POD 2, 3, 7, 14, 60 and 180 days, postoperative narcotic requirements, PACU and inpatient length of stay, complications, and readmission rates.

Chi-squared or Fisher's exact tests (where appropriate) were used to compare categorical variables, and Wilcoxon rank sum tests were used to compare continuous variables between treatment groups. Linear mixed effects regression models were used to assess treatment group differences in terms of pain scores, number of pills taken post-operatively, and PCS scores. Random effects were included to account for the longitudinally correlated nature of repeat assessments within a patient over time. All tests were two-sided and assessed for significance at the 5% level using SAS v9.4 (SAS Institute, Cary, NC).

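### Does the lack of a time window for postoperative narcotic use leave its comparison confounded with length of stay?

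*SAP*

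**What the plan says.** The SAP's Statistical Plan, first paragraph, ends its list of secondary outcomes with "postoperative narcotic requirements, PACU and inpatient length of stay, complications, and readmission rates". It attaches no start, end or setting to the narcotic outcome. The second paragraph states that "Wilcoxon rank sum tests were used to compare continuous variables between treatment groups", with no adjustment for time observed. It then lists the outcomes for the linear mixed models, which include "number of pills taken post-operatively, and PCS scores", with random effects for repeated assessments within a patient. It does not say which drug or period the pill count covers.

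The protocol supplies the unit but no period: "We will also measure intraoperative and post-operative narcotic use (converted to morphine equivalents"). Its one in-hospital time limit is in the pain-score schedule: "every 4 hours for the first twenty four hours or on discharge (whichever time-point occurs sooner"). After discharge, average pain is collected on "post-op day (POD) 2,3,5 and 7 via patient communication electronic message in RedCap".

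**The concern.** An in-hospital total depends on how long the patient is in hospital. The protocol's pain schedule allows for discharge before 24 hours, and the SAP makes "PACU and inpatient length of stay" an outcome, so the plan treats a difference in stay as possible. If the narcotic outcome were summed to discharge, the arm that left sooner would seem to need less narcotic even at the same hourly rate. A real reduction could be hidden if the arm with lower use stayed longer. Borrowing the pain schedule's limit would not fully cure this, because early discharge would still shorten the period. A window left open could also be chosen after the results are seen. At stake is the reading of one secondary outcome, and any claim that block timing spares narcotics.

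**Working it through.** **The plan's own figure.** The only figure near this point is N = 34 for the primary pain comparison (difference 2, SD 2, two-sided 5%, 80% power).

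- Normal approximation: n per arm = 2 × (1.960 + 0.842)² × (2/2)² = 15.7, so 16 per arm and 32 in total.
- Exact t-test at 17 per arm: noncentrality = 2 / (2 × √(2/17)) = 2.92 on 32 degrees of freedom, power 80.7%. At 16 per arm it is 78.1%.

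So 34 reproduces, and the narcotic question does not touch it.

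**The mechanism.** If use is constant, in-hospital total = hourly rate × hours in hospital. At equal rates the ratio of totals equals the ratio of stays, so a stay 25% longer gives a total 25% larger. The documents give no stay or narcotic data. Every input below is therefore an assumption, except 17 per arm, the 5% level and the Wilcoxon test.

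*Simulation A.* Mean rate 1.5 morphine equivalents per hour in both arms, between-patient CV 0.4 to 0.8, mean stay 24 h in one arm, stay CV 0.2, 4,000 trials per setting. Two-sided rejection rates:

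| Stay ratio | Mean totals | Wilcoxon on total | Wilcoxon on hourly rate |
|---|---|---|---|
| 1.0 | 36 vs 36 | about 5% | 4–6% |
| 1.1 | 36 vs 40 | 7–10% | 4–6% |
| 1.25 | 36 vs 45 | 13–30% | 4–6% |
| 1.5 | 36 vs 54 | 33–73% | 4–6% |
| 2.0 | 36 vs 72 | 74–99% | 4–6% |

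*Simulation B.* Group I median stay 24 h, stay CV 0.25, use CV 0.3, 0.5 or 0.8, use constant or halving every 12 h, correlation of stay with use −0.5, 0 or +0.5, 20,000 trials per setting. Share of trials with significantly lower use in Group II at an equal underlying rate (2.5% expected), for the total to discharge:

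| Group II stay | Range over grid |
|---|---|
| equal | 2.3–2.7% |
| 10% shorter | 3.4–18.2% |
| 20% shorter | 5.8–61.2% |
| 30% shorter | 9.6–94.7% |

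**Where the large figures come from.** At 20% shorter, the 61% needs low variability (CV 0.3), constant use and heavier users leaving sooner (correlation −0.5), all at once. Moving only the correlation to 0 or +0.5 gives about 36% or 26%. In the middle of the grid (CV 0.5, correlation 0) the figure is 21% with constant use and 9% with halving use. If the total is capped at 24 h and the median stay is 36 h, it is 2.6–4.5%.

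**What the candidate remedies cost**, at a 20% shorter stay:

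- A fixed 24 h window holds 2–3%, but only if doses taken at home are fully recorded. If half the home use is missed, the figure is about 3.4–8.5% at correlation 0.
- A window ending at the shortest stay in the trial would last about 12 h (5th to 95th percentile about 10–15 h), which discards much of the data.
- Use per hour holds 2–3% if use is constant. If use falls with time it errs the other way, with up to 22% of trials showing significantly more use in Group II.

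**The passages side by side.** The arithmetic needs two premises. The first is that the outcome is a total that stops at discharge. Neither document says so: the protocol's narcotic sentence has no end point, the limit of 24 hours or discharge belongs to pain scores, and the SAP's repeated pill counts suggest that some use may be recorded after discharge. The second is that stays differ between arms. Listing length of stay as an outcome allows for that but gives no reason to expect it.

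**The case for a change.** The strongest case for a change is that the gap is in the text and does not depend on any simulation. A narcotic outcome without a period is incomplete, and the plan itself lists the variable that could distort it. The pill count does not settle the matter, because it has no stated drug, period or link to morphine equivalents. Reporting length of stay would alert a reader (at a 20% shorter stay its own test is significant in about 70% of trials in simulation B) but would not correct the narcotic comparison. A fixed window would cost little: one phrase in the SAP and one item in a message already sent on day 2.

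Part of this stands. The period, the setting and the relation to pill count are unstated, and an in-hospital total would mix rate with time if stays differed. The step to a required change does not stand. The total given during the stay is itself a legitimate randomised comparison: if one arm leaves sooner and receives less in hospital, that difference is real. It misleads only if read as a rate or as use over a fixed period. The proposed window is borrowed from the pain schedule, and other fixed windows would be as defensible. The SAP is written in the past tense, so a new data item may no longer be possible.

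**Conclusion.** No change to the plan is called for. This is a missing definition for one secondary outcome, which analysts can fill sensibly; it is not a stated rule that gives a wrong answer. Naming the period and setting when the result is reported, and reading any in-hospital total beside length of stay, is ordinary practice. A fixed window, a rate and an in-stay total each have a cost, and reasonable statisticians would differ on which to prefer.

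The possible distortion is nil with equal stays. With an in-hospital total and one arm's stay 20% shorter, it is about 9–21% against 2.5% expected in the middle of the assumed grid. Larger values need low variability together with constant use and heavier users leaving early, or larger differences in stay. Its actual size and direction cannot be known from the documents, which give no stay or narcotic data. The conclusion rests on the documents not defining the outcome as a total to discharge and giving no reason to expect unequal stays.

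### Does naming only postoperative narcotic use as an opioid outcome leave the SAP unable to interpret an opioid difference?

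*SAP*

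**What the plan says.** The SAP's Statistical Plan lists, among the secondary outcomes, "postoperative narcotic requirements, PACU and inpatient length of stay, complications, and readmission rates". Neither intraoperative nor total perioperative narcotic use appears there. The one other medication measure is in the sentence on mixed models, which covers "treatment group differences in terms of pain scores, number of pills taken post-operatively, and PCS scores"; it too is postoperative and is not identified as opioid. For everything else on a continuous scale the SAP gives a general rule: "Wilcoxon rank sum tests were used to compare continuous variables between treatment groups".

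The protocol collects more: "We will also measure intraoperative and post-operative narcotic use (converted to morphine equivalents" is its commitment on opioids. On the arms it says "Group I will have the block performed after induction of general anesthesia and prior to surgical incision by the anesthesiologist", and "Group II will have the block administered by the surgeon after mastectomy is performed and before reconstruction".

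**The concern.** Timing of the block relative to the mastectomy is the randomized factor. Group I has its mastectomy with the study block in place and Group II does not, so the contrast between arms is present during an intraoperative phase that the named opioid outcome leaves out. If the arms receive different amounts of intraoperative opioid, a postoperative difference could mean that less was used overall, or only that use moved into or out of the operating room.

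At stake is the reading of one secondary outcome: a report could present a postoperative reduction as opioid sparing when the total had not changed. Leaving intraoperative use off the list also leaves some freedom, after the data are seen, over whether and how to report it.

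**Working it through.** **1. The plan's own figure.** Inputs from the SAP: difference 2, SD 2, two-sided 5%, 80% power, 1:1 allocation. The normal approximation gives n per arm = 2 × (1.96 + 0.842)² × (2/2)² = 15.7, so 16 per arm and 32 in total. The exact two-sample t-test calculation gives 16.71, so 17 per arm and 34 in total, with power 80.7% (78.1% at 16 per arm). The SAP's 34 is reproduced. It is set by the pain score, and no choice of opioid outcome alters it.

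**2. What a postoperative difference can show.** For each patient, total = intraoperative + postoperative, so the mean difference in total equals the intraoperative difference plus the postoperative difference. A known postoperative difference fixes neither the size nor the sign of the total. To that extent the concern is right. The documents give no opioid mean or SD, so the size of any shift cannot be calculated.

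**3. Is intraoperative use outside the analysis?** Set the two documents side by side:
- The protocol commits to measuring it, in morphine equivalents.
- It is a continuous variable, and the SAP assigns the Wilcoxon test to continuous variables compared between groups.
- The secondary list is not the limit of what is analysed. Pill counts and PCS scores are modelled in the SAP, yet neither is on that list.

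Absence from the list therefore does not show that intraoperative use will go unanalysed. What is missing is a label and a derived total.

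**4. What the extra outcomes would deliver.** Assume 17 per group, normal data and equal SDs.
- One opioid component: 95% CI half-width = t(0.975, 32) × √(2/17) = 2.037 × 0.343 = 0.70 SD.
- Simulated Wilcoxon power (normal shift, 8,000 runs per value): 27.9% for 0.5 SD, 54.2% for 0.75 SD, 77.7% for 1.0 SD.
- Total, with equal component SDs and an assumed within-patient correlation r between phases: SD(total) = SD × √(2(1 + r)).

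| Assumed r | SD of total (component SDs) | 95% CI half-width (component SDs) |
|---|---|---|
| -0.3 | 1.18 | 0.83 |
| 0 | 1.41 | 0.99 |
| 0.3 | 1.61 | 1.13 |

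Now take an observed postoperative difference of -0.70 SD, about the smallest whose interval excludes zero, and suppose no intraoperative offset is observed. The total difference is then also -0.70 component SDs, and its upper limit is -0.70 + 0.83 = 0.13, -0.70 + 0.99 = 0.29 or -0.70 + 1.13 = 0.43 for the three correlations. All three intervals include zero. Even with no observed shift, the total would not confirm a net saving.

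**5. Cost of formal tests.** Two added comparisons at 5% carry a chance of at least one false positive of at most 2 × 0.05 = 10%.

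**The case for a change.** The best case for a change is that a general rule assigns a test to a type of variable but does not name an outcome. Naming intraoperative and total morphine equivalents in advance would remove discretion over what is reported, would use data already collected, and would cost a sentence and one derived variable. A total also has to be built per patient, since medians do not add. Low power is no reason for silence if an estimate and interval are given.

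Part of this stands. The omission is real, and a postoperative difference should not be described as a saving in total opioid. A sensible analyst would tabulate intraoperative use by group beside the postoperative result, and both documents already permit that.

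The case for requiring the total is weaker than it looks, for two reasons beyond precision. First, the protocol blinds the patient and the research assistant collecting the data. It does not list the anesthesiologist as blinded, and the anesthesiologist performs the Group I block. Intraoperative opioid may therefore be given by staff who know the allocation, and a difference in the total could partly reflect that knowledge. Second, the protocol gives no time window for postoperative narcotic use, and the SAP treats PACU and inpatient stay as outcomes. A total running to discharge would cover different lengths of time in different patients, and a common cut-off would first have to be defined.

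**Conclusion.** No change to the plan is needed. The SAP answers the postoperative question it sets, and neither document states an aim of reducing total opioid use. The postoperative narcotic comparison is valid for postoperative use, and the primary endpoint, its test and N = 34 (80.7% power by exact calculation) are untouched. What remains is a gap in labelling that analysts can fill from data the protocol already collects and with a test the SAP already specifies.

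The consequence of the gap has no computable size, because no opioid figures are given. The gain from closing it formally would be small: half-widths of 0.70 SD for a component and 0.83 to 1.13 component SDs for a total, assuming normal data, equal SDs and correlations between -0.3 and 0.3. The judgment would differ if the trial claimed a net opioid saving as an objective; on the text as it stands, it does not.
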